- Time (measured in whole days) until drain removal and drain output (quantity and contents) on day of removal. Daily output will be calculated adding up the volumes drained in the 24 hours prior to the morning ward round. Contents are defined as serous fluids (with or without blood staining), frank blood, purulent and faecal.
- Overall 30-day adverse event rate as defined by the Clavien-Dindo scale of postoperative complications (25) and length of stay (days).

- ▲ Day of surgery is defined as Post-operative Day (POD) 0. The day after surgery is therefore defined as POD 1 and day 10 after surgery as POD 10. ▲

8. Measuring drain output

Drain output (volume and contents) should be assessed daily until removal or for the first ten days after surgery (Day 0: day of surgery – Day 10).

Strategies to record drain output and day of drain removal

- Speaking to ward staff, including doctors and nurses
- Reviewing patient notes daily, particularly drain charts
- Participating in daily ward rounds and doctor reviews

Remember: recordings of drain output must correspond to the entire day (8am to 8am). It is advised that you collect data one day in retrospect to capture all relevant data.

9. Covariates

Data will be collected on audit standards, and confounding factors for risk of intra-abdominal postoperative complications to permit accurate risk adjustment of outcomes. Without appropriately adjusting for risk factors, it is likely that any findings would be biased and unable to be appropriately analysed on a national scale. Data will **not** be analysed at a surgeon-level or centre-level. A full list of required data fields is available in Appendix A, and on the REDCap database.

10. Follow-up

Patients will be followed for 30 days after surgery. All secondary outcome measures will be recorded if they occurred at any point from postoperative Day 0 (day of surgery) to Day 30.

No change to routine follow up should take place. Collaborators should be proactive in identifying follow up data, but this should be done within the limits of routine follow up.

Strategies for follow-up include:

- Regularly reviewing patient notes to identify in-hospital complications.
- Participating in daily ward rounds and doctor reviews.
- Reviewing clinic notes and clinic letters, if seen in clinic by 30 days.
- Checking electronic systems and handover lists for re-admissions.
- Checking for emergency department re-attendances.

11. Data Analysis & Sample Size

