Project team structure: Medical students will take the lead in disseminating and delivering this study alongside junior doctors. These ‘mini-teams’ should be supervised by a consultant surgeon at each site (Figure 1). Each team should include at least one qualified doctor to provide additional local support for participating medical students.

Training: The protocol was formally launched at the European Society of Coloproctology (ESCP) meeting on 26th September 2019. Investigators will be trained in the study background, design, and methodology. COMPASS regional and local leads are encouraged to hold local meetings with collaborating teams at their medical school to brief them on the protocol, and to feedback any local issues or questions raised. To ensure collaborators understand the study topic, drain follow-up, inclusion criteria, application of the Clavien-Dindo classification and the principles of data governance, they will all be asked to complete a series of online e-learning modules (pass mark is 100%) prior to starting data collection.

Data completeness: Following data collection, only data sets with >95% data completeness will be accepted for pooled analysis. To emphasise the importance of data completeness to collaborators, centres with >5% missing data points will be excluded from the study and collaborators from those centres withdrawn from the published list of citable collaborators.

Validation: Data validation will be performed at a minimum of five centres in each participating country. Data validators may be either a final year student or a qualified doctor who were not involved in the initial data collection.

The validator will be assigned a random 2-week data collection period at a local centre to validate. Data validation will occur following completion of data collection (including follow-up). After completing validation, the validator will send a summary of how many records were reviewed and error rates to the study management group. There are two components of validation:

I. Case ascertainment:

- The validator will independently identify all patients eligible for inclusion over the one 2-week study period. The target for data ascertainment is >95%.

II. Data collection

- The validator will independently collect data for the key data fields relating to risk-adjustment and outcome measures (see **Appendix A**).

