Surgical site infection type	Yes - Superficial (skin or subcutaneous tissue) / Yes - Deep (fascial and muscle layers) / Yes - Organ/Space SSI (intrabdominal) / No .
Small bowel evisceration/herniation of omentum	Yes – Site of Drain(s) / Yes – Other incision / No Prolapse of small bowel and/or omentum through an incision.
Drain-related iatrogenic bowel perforation	Yes - Intraoperative / Yes – Postoperative (not during removal) / Yes – Postoperative (during removal) / No.
Drain-related skin irritation	Yes (reversible damage of the skin at the drain insertion site associated with rash, dry skin, itchiness, red discolouration and/or hives) / No
Other Drain-related complication	Please specify
Reason(s) for drain removal	
1. Clinical rationale:
 
a). Drain output satisfactory (Yes, No) - if yes: low volume, (haemo)serous fluid, other (please specify).
 
b). Drain-related complications.
 
c). Inadvertent/premature drain withdrawal.
 
d). Other (please specify)
 
2. Radiological confirmation of no significant ongoing collection (Yes - pre removal, Yes - post removal, No).

Post-operative blood transfusion	Yes / No
Day of blood transfusion	Post-operative Day (POD)
History of collection(s) requiring treatment within 30 days (either medical, surgical, endoscopic, radiological)	Yes / No
Day of collection(s) identification	Post-operative Day (POD)

Collection(s) identification method	
1. Clinical only
 
a). Symptoms. b). Change in drain output (if inserted at time of surgery).
 
2. Radiological
 
a). Imaging due to clinical suspicion b). Routine imaging as per hospital policy c). Incidental finding (imaging for other indication).

Collection(s) treatment	
Conservative management (none or antibiotic therapy) Percutaneous drainage Surgery

Total postoperative antibiotic duration	
Number of days (Total antibiotic duration including both intravenous and oral antimicrobial therapy for the treatment of the collection(s). Post-operative antimicrobial therapy started before the identification of the collection(s) should not be included.)

Outcome data points	Required data (definition / comment)
Anastomotic leak within 30 days	Yes - Radiological diagnosis / Yes - Surgical diagnosis / No
Day of anastomotic leak diagnosis	Post-operative Day (POD)
Length of hospital stay (days)	Days
30 day readmission	Yes / No

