Appendix C: Clavien-Dindo classification system

Adverse post-operative events may be divided up into treatment failures, sequelae and complications.

- **Failure of treatment** occurs when the original surgery fails to achieve its intended benefits; for example, persistent pain following laparoscopic cholecystectomy or tumour recurrence following cancer surgery.
- **Sequelae** are the recognised consequences of a given procedure; for example, gut malabsorption following a large small bowel resection or immune deficiency following splenectomy.
- **Complication:** Any deviation from the normal post-operative course that has an adverse effect on the patient and is not either a treatment failure or sequel.

In the Clavien-Dindo classification (13), the factor determining the severity of a complication is the treatment required. Consequently, a given complication may be graded differently depending on how it has been managed. For example, an anastomotic leak may be managed just with antibiotics if it is contained (grade II) or it may require re-operation under anaesthetic (grade III).

Some other considerations:

Intra-operative complications are not considered unless they have an adverse effect on the patient post-operatively. The only exception to this is **intra-operative death**; this is classified as grade V.

All post-operative adverse events are included, even when there is no direct relationship to the surgery.

All adverse events within the follow-up period (30 days) are included, even if they occur following discharge.

Diagnostic procedures are not included. For example, a diagnostic oesophagoduodenoscopy (OGD) to look for a source of bleeding without any intervention would not be considered a complication, but a therapeutic OGD with clipping of a bleeding vessel would be considered a grade III complication. Since **negative exploratory laparotomies** are considered to be diagnostic procedures, they should not be recorded as complications.

Grade	Definition (examples listed in italics)

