data, it will be particularly helpful if the consultant is present to offer guidance regarding this.

7. **Identify all** patients meeting **inclusion criteria** within your 14-day period.

8. Regularly **follow-up** for information on complications over the **30-day post-operative period**. This study is a prospective study, so you should not wait until the end of the post-operative period to follow-up patients. Discuss the best way to follow up patients with the consultant supervising your audit, as this will vary from centre to centre.

9. Ensure all data has been uploaded to the **REDCap** system and you have completed all fields, avoiding **missing data points**. If more than 5% of patients at your centre are missing data, your centre cannot be included and your name will be withdrawn from the author list.

It is a **condition** of participation in the COMPASS study that following completion of the audit at your centre you **must** ensure that your **local results are presented** to your hospital's surgical department.

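### Thirty-day outcomes rest on routine follow-up with no code for 'not known after discharge', and blanks are penalised, so unobserved patients are likely to be stored as event-free

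*Protocol*

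**What the plan says.** Section 10 sets the window: "All secondary outcome measures will be recorded if they occurred at any point from postoperative Day 0 (day of surgery) to Day 30". It allows no change to routine follow-up and adds: "Collaborators should be proactive in identifying follow up data, but this should be done within the limits of routine follow up". After discharge the suggested sources are conditional or passive. They are "Reviewing clinic notes and clinic letters, if seen in clinic by 30 days", a search of electronic systems and handover lists for readmissions, and "Checking for emergency department re-attendances". No status check at day 30 is required. Appendix D, step 8, leaves the method to each centre: "Discuss the best way to follow up patients with the consultant supervising your audit, as this will vary from centre to centre".

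Appendix C nevertheless sets a complete 30-day standard: "All adverse events within the follow-up period (30 days) are included, even if they occur following discharge".

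Section 9 calls Appendix A the full list of required fields. There, collection within 30 days and readmission are Yes or No, leak has two Yes categories or No, and the highest complication grade is None or I to V. None has an unknown option, and no date of last contact or follow-up status is listed. Elsewhere the dictionary does allow for absent information: the air leak test has a not-recorded category, and HIV a combined no/unknown one.

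Missing data carry a penalty. Section 14 says "centres with >5% missing data points will be excluded from the study" and removes those centres' collaborators from the citable list. Section 15 applies a 95% completeness rule to each data collection period. Appendix D, step 9, excludes a centre when more than 5% of its patients have missing data.

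**The concern.** Take a patient discharged on day 4 and not seen again at the operating hospital by day 30. The team does not know whether a collection was treated elsewhere. The form offers 'Yes', 'No' or a blank. 'Yes' has no basis, and a blank counts towards exclusion and loss of authorship, so 'No' is the easy entry. The database then holds the same record for this patient as for one seen well in clinic on day 30.

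Two secondary results are exposed. The 30-day rates (collections, surgical site infection, overall adverse events) are under-counted, and the loss grows as stay shortens. If drained and undrained patients differ in stay, part of any difference in rates reflects how long each group was watched. Recorded time to diagnosis is also pulled early, because the diagnoses that go missing are those made after discharge. Detection timing by drain placement is a stated secondary aim.

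This cannot be left to an analysis plan: follow-up status that was never collected cannot be rebuilt afterwards.

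**Working it through.** The protocol states no event rate, length of stay or expected loss to follow-up, so there is no figure of its own to reproduce here. Two things can be checked: the strength of the incentive, from the protocol's own numbers, and the possible size of the bias, on assumptions.

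**1. Incentive under each missing-data rule**

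Section 11 expects three resections per week per centre. Over one 14-day period that is 3 × 2 = 6 patients. Stoma formations and reversals are also eligible, so true counts may be higher.

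*Per-patient rule (Appendix D, step 9; limit 5%).* Share with one blank patient = 1 / n:
- one period: 1/6 = 16.7%
- two periods: 1/12 = 8.3%
- three periods: 1/18 = 5.6%
- four periods: 1/24 = 4.2%

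A centre needs at least 20 patients before it can leave one incomplete.

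*Data-point rule (section 14; limit 5%).* Appendix A has about 41 unconditional fields for an undrained patient (my count). Leaving collection, leak, readmission and grade blank is 4/41 = 9.8% of that patient's fields. A centre that is otherwise complete crosses 5% when 5/9.8, or about half, of its patients are blank on all four.

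The pressure is therefore strong under the Appendix D rule and weak under the section 14 rule. Appendix D is the checklist addressed to the people entering data.

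**2. Effect on rates (all inputs assumed)**

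Observed rate = true rate × [F(L) + c × (1 − F(L))], where F is the distribution of diagnosis day, L the length of stay and c the share of post-discharge events that are captured. Assume a true 30-day rate of 8% in both groups, stays of 5 and 9 days, and a gamma-distributed diagnosis day truncated at day 30.

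With mean 7 and SD 4, F(5) = 0.417 and F(9) = 0.773. At c = 0.5:
- short stay: 8 × (0.417 + 0.5 × 0.583) = 5.67%
- long stay: 8 × (0.773 + 0.5 × 0.227) = 7.09%
- ratio 1.25, when the truth is 1

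| c | mean 7, SD 4: short v long stay (ratio) | mean 9, SD 6: short v long stay (ratio) |
|---|---|---|
| 1.0 | 8.00 v 8.00 (1.00) | 8.00 v 8.00 (1.00) |
| 0.9 | 7.53 v 7.82 (1.04) | 7.46 v 7.70 (1.03) |
| 0.7 | 6.60 v 7.46 (1.13) | 6.39 v 7.10 (1.11) |
| 0.5 | 5.67 v 7.09 (1.25) | 5.31 v 6.50 (1.22) |

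A simpler calculation assumes that 30% of collections in drained and 50% in undrained patients surface after discharge, and that a quarter to a half of those are not seen. Capture is then 0.925 v 0.875 (ratio 1.06), or 0.85 v 0.75 (ratio 1.13).

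**3. Effect on time to diagnosis (same assumptions as step 2)**

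At c = 0.5 the recorded mean falls in both stay groups:
- from 6.99 days to 5.98 (short stay) and 6.25 (long stay)
- from 8.82 days to 7.47 (short stay) and 7.46 (long stay)

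The gap between groups is at most about 0.3 day. Its direction is not stable: at c = 0.7 the means are 6.47 v 6.57 under the first distribution and 8.15 v 8.07 under the second.

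**The case against.** Several counter-arguments have force.

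- A reader might infer that the protocol tells sites to enter 'No'. It does not. That entry is inferred from the form and the penalties, and the data-point rule tolerates many blanks. This stands, and it is why the conclusion is worded as likely.
- A reader might infer that only the operating hospital's records are searched. The section 10 list is open-ended, and electronic systems may reach further at some centres. Readmission and emergency checks should also recover many serious events. This stands and limits the loss, but it does not record who was actually observed.
- A reader might infer that no sensitivity analysis is possible. Length of stay, day of collection, day of leak, readmission and day of death are all collected, so an analysis of in-hospital events is feasible. What cannot be separated is an event-free patient from one not observed after discharge.
- Independent validation re-collects outcome fields against a target above 98%. It can catch a 'No' entered without checking. It names no further follow-up source, so it would tend to agree with a 'No' for an event recorded nowhere locally.
- The routine-care limit is deliberate in an audit that must not alter pathways. That is accepted; the remedy needs no patient contact.
- Sampling error may be as large as the bias. With an assumed 150 events in each of two groups of 2,500, the SE of the log ratio is √(2/150 − 2/2500) = 0.112, a 95% factor of exp(1.96 × 0.112) = 1.25. The comparison is fair, but a systematic error is not reflected in the confidence interval.
- The case report form and REDCap screens are not shown and might carry an unknown code. The point rests on Appendix A.

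**Conclusion.** The point holds as a design weakness in the secondary outcomes that should be corrected. Ascertainment limited to routine follow-up, no code for unknown status and a penalty for blanks together make it likely that unobserved patients are stored as event-free. Thirty-day rates are then biased downward, more so after short stays. Comparisons by drain are affected only if stay differs between the groups, which the documents do not establish.

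The size cannot be derived from the documents. The range of 1.03 to 1.25 rests wholly on assumed rates, stays, diagnosis times and capture shares, and shows only that the effect need not be negligible. A reader might infer that the earlier-detection comparison is seriously distorted. The figures do not support that: recorded times shift early in both groups, but the difference between groups is about 0.3 day at most and of uncertain sign. Drain insertion, which the primary outcome measures, is recorded at surgery and is unaffected.

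**What to change.** Add to Appendix A a follow-up-status entry made of two short fields: the last postoperative day (up to 30) on which the patient's status was known, and the source of that knowledge. Keep a negative record search separate from direct contact such as a clinic visit. Otherwise a patient treated elsewhere would still be recorded as known to be well.

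Add an 'unknown after discharge' code to collection, leak, readmission and complication grade. State in sections 14 and 15 and Appendix D that it counts as a complete answer for the 95% rule.

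Report the share with known day-30 status by drain group. Add sensitivity analyses restricted to in-hospital events, and bounds on the unobserved share.

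Do not make censoring at the last-known day the main analysis. Patients with events come back and well patients do not, so that censoring is informative. As an assumed example, take 2,500 discharged patients, 75 later events all captured and 1,000 patients with any later contact. The crude post-discharge risk becomes 75/1,000 = 7.5% instead of 75/2,500 = 3%.

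The cost is two short fields per patient, one extra response code on four items and a sentence in the completeness rules. No patient contact or change of pathway is needed. Missed events are not recovered, and the stated 30-day completeness will look less favourable.

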Appendix A: Data Dictionary

Please use the case report form together with this Data Dictionary to facilitate data collection

Preoperative data points	Required data (definition / comment)
Patient age	Years (whole years at the time of operation)
Patient gender	Male / Female
Patient ASA grade	Grade I-V (Full ASA classification available at: https://www.asahq.org/resources/clinical-information/asa-physical-status-classification-system).
Smoking status	Current (includes those who stopped smoking within 6 weeks), Previous , Never .
Patient height	Meters (record to two decimal places)
Patient weight	Kilograms (record to one decimal places)
Body Mass Index (if either weight or height unknown)	Underweight (<18.5), Normal range (18.5-24.9), Overweight (25-30), Obese (>30).
History of abdominal surgery	Yes / No
Pre-existing abdominal stoma	Yes – colostomy / Yes – jejunostomy or ileostomy / No stoma
History of ischaemic heart disease	Yes (Myocardial infarction or Angina) / No
History of congestive heart failure	Yes / No

History of cerebrovascular disease	Yes (transient ischemic attack or stroke) / No
History of diabetes mellitus	Yes (Type 1) / Yes (Type 2) / No
Control of diabetes mellitus	IF diabetes mellitus present Yes, insulin controlled / Yes, tablet controlled / Yes, diet controlled / No
Last pre-operative blood test values	Haemoglobin (grams / litre) / White Cell Count ($\times 10^9$ / litre) / estimated Glomerular Filtration Rate (ml / min) / C Reactive Protein (milligrams / litre).
History of immunosuppression	HIV (antiretroviral therapy, no/unknown), Steroids (yes: oral, intravenous or topical e.g. prednisolone, fludrocortisone, dexamethasone, no), Other immunosuppressive drug (yes, e.g. azathioprine, methotrexate, biologic agents, no), Chemotherapy (yes, current chemotherapy or if the last cycle was within 12 weeks of operation, no).
Operative data points	Required data (definition / comment)
Underlying pathology/indication	Malignancy / Inflammatory bowel disease / Diverticular disease / Bowel ischaemia / Small bowel obstruction / Large bowel obstruction / Other benign
Perforated bowel	Yes / No
Operative urgency (NCEPOD Classification of Intervention, available at https://www.ncepod.org.uk/classification.html)	Immediate (Immediate life, limb or organ-saving intervention – resuscitation simultaneous with intervention. Normally within minutes of decision to operate). Urgent (Intervention for acute onset or clinical deterioration of potentially life-threatening conditions, for those conditions that may threaten the survival of limb or organ, for fixation of many fractures and for relief of pain or other distressing symptoms. Normally within hours of decision to operate) Expedited (requiring early treatment where the condition is not an immediate threat to life, limb or organ survival. Normally within days of decision to operate). Elective (Intervention planned in advance of routine admission to hospital)
Operative contamination	Clean-Contaminated (Gastrointestinal (GI) and genitourinary (GU) tracts entered but no gross contamination). Contaminated (GI or GU tracts entered with gross spillage or major break in sterile technique).

	Dirty (There is already contamination prior to operation, e.g. faeces or bile).
Operative approach	
Open (performed exclusively using instruments inserted in to the abdomen through a surgical incision). Laparoscopic (performed exclusively using instruments inserted in to the abdomen through small ports) or Laparoscopic-assisted (laparoscopic surgery in which an incision is enlarged to deliver a specimen or to insert a gloved hand into the abdomen). Laparoscopic converted to open (surgery planned to be performed laparoscopically but for unforeseen reasons the decision was made to change to an open approach). Robotic (robot-assisted surgery with no conversion to either laparoscopic or open approaches). Robotic converted to open (surgery planned to be performed robotically but for unforeseen reasons the decision was made to change to an open approach).

Primary operation performed	Select main procedure from Appendix B (closest option from the drop-down list or enter as free text by selecting "other").
Anastomosis creation	Yes – intraperitoneal / Yes – extra peritoneal / No
Stoma formation	Yes – colostomy / Yes – jejunostomy or ileostomy / No stoma
Documented air leak	Recorded (positive) / Recorded (Negative) / Not recorded
Duration procedure	Minutes (from knife-to-skin to closure of skin).
Intraoperative blood transfusion	Yes / No
Intraoperative complications	None / Vascular injury / Bowel injury (e.g. duodenum) / Injury to other organs or structures (e.g. ureter)
Abdominal drain(s) inserted at time of surgery	Yes / No
Reason for drain identified	
Not identified Excessive intraoperative blood loss (or concern regarding this). Excessive intraoperative fluid (not blood) collections (or concern regarding this). Contaminated or dirty surgery

	
Positive air leak test (the intra-operative air leak test is a common intraoperative test used to identify mechanically insufficient anastomosis)
 
Poor vascularisation of the anastomosis (determined visually or by ICG fluorescence) (or concern regarding this).
 
Other reason identified (please specify)

Number of drains	Number
Type of drain(s) used	
Open (open drains drain fluid on to a gauze pad or into a stoma bag e.g. Penrose) / Close (tubes draining into a bag or bottle, e.g. Jackson-pratt).
 
Active (drains maintained under suction) / Passive (drains that have no suction and work according to the differential pressure between body cavities and the exterior).
 
(see REDCap for pictures)

Drain location	
Subcutaneous drain
 
Intraabdominal drain – pelvis
 
Intraabdominal drain – peritoneal cavity
 
Intraabdominal drain – posterior to the anastomosis
 
Intraabdominal drain – anterior to the anastomosis
 
Intraabdominal drain – near the anastomosis (not in contact)

Daily postoperative data points (to be completed for each inserted drain)	Required data (definition / comment)
Day of surgery is defined as Post-operative Day (POD) 0. The day after surgery is therefore defined as POD 1 and day 10 after surgery as POD 10.	
Volume drained (Daily POD 1-10)	
Millilitres (recordings of drain output must correspond to the entire day, i.e. 8am to 8am).
 
It is recommended that you collect data one day in retrospect.

Contents of drain output (Daily POD 1-10)	
Serous fluid (with or without blood staining) / Frank blood / Purulent / Faecal
 
(see REDCap for pictures)

Drain-related data points	Required data (definition / comment)

Day of drain removal	Post-operative Day (POD)
Surgical site infection	Yes – Site of Drain(s) / Yes – Other incision / No As defined by US Centers for Disease Control and Prevention (CDC)
Surgical site infection type	Yes - Superficial (skin or subcutaneous tissue) / Yes - Deep (fascial and muscle layers) / Yes - Organ/Space SSI (intrabdominal) / No .
Small bowel evisceration/herniation of omentum	Yes – Site of Drain(s) / Yes – Other incision / No Prolapse of small bowel and/or omentum through an incision.
Drain-related iatrogenic bowel perforation	Yes - Intraoperative / Yes – Postoperative (not during removal) / Yes – Postoperative (during removal) / No.
Drain-related skin irritation	Yes (reversible damage of the skin at the drain insertion site associated with rash, dry skin, itchiness, red discolouration and/or hives) / No
Other Drain-related complication	Please specify
Reason(s) for drain removal	
1. Clinical rationale:
 
a). Drain output satisfactory (Yes, No) - if yes: low volume, (haemo)serous fluid, other (please specify).
 
b). Drain-related complications.
 
c). Inadvertent/premature drain withdrawal.
 
d). Other (please specify)
 
2. Radiological confirmation of no significant ongoing collection (Yes - pre removal, Yes - post removal, No).

Post-operative blood transfusion	Yes / No
Day of blood transfusion	Post-operative Day (POD)
History of collection(s) requiring treatment within 30 days (either medical, surgical, endoscopic, radiological)	Yes / No
Day of collection(s) identification	Post-operative Day (POD)

Collection(s) identification method	
1. Clinical only
 
a). Symptoms. b). Change in drain output (if inserted at time of surgery).
 
2. Radiological
 
a). Imaging due to clinical suspicion b). Routine imaging as per hospital policy c). Incidental finding (imaging for other indication).

Collection(s) treatment	
Conservative management (none or antibiotic therapy) Percutaneous drainage Surgery

Total postoperative antibiotic duration	
Number of days (Total antibiotic duration including both intravenous and oral antimicrobial therapy for the treatment of the collection(s). Post-operative antimicrobial therapy started before the identification of the collection(s) should not be included.)

Outcome data points	Required data (definition / comment)
Anastomotic leak within 30 days	Yes - Radiological diagnosis / Yes - Surgical diagnosis / No
Day of anastomotic leak diagnosis	Post-operative Day (POD)
Length of hospital stay (days)	Days
30 day readmission	Yes / No
Highest 30-day complication grade	
None / Clavien-Dindo Grade I-V (see Appendix C for the full Clavien-Dindo scale).
 
For Grade V please collect: Death during primary admission? Yes/No Postoperative day of death: _____ day

